**c. Screening**

Participants who pass pre-screening will be invited to participate in the study and scheduled for consent and formal screening.

Upon arrival to the screening appointment, written, informed consent will be obtained by an investigator and formal screening will be done according to Appendix A.

Volunteers who have not had a neurological exam from an NINDS provider within the past two years will receive a neurological examination from an NINDS physician or nurse practitioner. This will not replace any exam the participant will receive for purposes of medical care; the exam will be for research purposes only. All women of child-bearing potential will have a urine pregnancy test (not earlier than 24 hours) before each MRI scan.

**d. Study procedures**

**ii. Behavioral Tasks**

Behavioral testing will occur at baseline, 24-hours, and two-weeks after stimulation.

Weather Prediction Task (feedback version; WPT-F) - This is a test of the ability to learn an implicit, stochastic, association by trial and error and recruits a brain network including the dorsolateral prefrontal cortex and the head of the caudate nucleus, primarily in the right hemisphere. In the WPT, participants learn to predict a binary outcome, based on arbitrary stimuli with a hidden statistical link to that outcome. One, two, or three-card combinations of four possible cards are presented on a computer and the subject is asked to predict the “weather;” i.e. whether it will be rainy or fine. After each prediction, the subject receives corrective feedback. Each card is independently associated with one outcome with a fixed probability. For example, the probability of rainy might be 0.2 for squares, 0.4 for diamonds, 0.6 for circles, and 0.8 for triangles. We will use three different versions of the task at the three test sessions (see below). The task has 200 trials, with breaks after every 50 trials.

Weather Prediction Task (Observational version; WPT-O) – The observational version of the WPT resembles a paired associates test where the feedback and cards are displayed on the screen are shown on the screen together. After all pairs are shown the cards are again shown and the participant is asked to remember which feedback outcome (rain or fine) goes with that set of cards. Unlike the WPT-I, the WPT-E recruits brain regions that support declarative memory. Both version each take approximately 20 minutes. The order of the tasks will be counterbalanced across participants.

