### **b. Secondary outcome measures**

- Pre-to-Post rTMS differences in WPT-O scores
- Pre-to-Post rTMS differences in WPT-F scores
- Pre-to-Post rTMS differences in rsFC and tbFC between memory networks.

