## **10. Statistical Analysis**

### **a. Analysis of data/ study outcomes**

Our primary aim is to examine stimulation-dependent changes in FC within the targeted network in each study. Secondary aims for this protocol will include all behavioral change data from the WPT-F and WPT-O and changes in FC to the non-targeted network, and between networks.

To calculate FC from resting-state scans, the Pearson correlation coefficients ( $r$ ) between time courses of BOLD activity in a seed region (i.e. hippocampus or striatum) will be calculated to determine the FC before and after rTMS stimulation. They will be Fisher-transformed to normalize  $r$ -values.

To calculate FC from task-based scans, the time series from a seed region will be inputted into a general linear model analysis as a regressor along with a regressor indicating when the task is occurring. For the WPT-F, this will include both the choice phase and the feedback phase during learning. For the WPT-O, this will include the observational trials and the retrieval trials. This analysis will be performed on each

individual to create a spatial map of beta values indicating the strength of the association between the seed and other regions during task performance.

*Statistical analysis for Experiments 1 and 3 (targeting the hippocampal network)*

iv. Preliminary Aims

Primary Aim 1

To confirm modulation of the hippocampal network, the average timeseries of the left hippocampal seed will be correlated with all other voxels with available data before and after stimulation. These data will be submitted to AFNI's 3dLME linear mixed effects function, which will be used to reveal potential areas of significant change in rsFC and tbFC.

v. Secondary Aims

Secondary Aims

Behavioral data will be submitted to a 3 x 2 x 2 ANOVA using timepoint (Pre-stimulation, post-stimulation, and follow-up), group (PPC vs. Vertex), and learning type (procedural and declarative) as factors. A significant interaction ( $p < 0.05$ ) between time, group, and learning type will confirm network-dependent modulation of each memory type.

To confirm changes in FC, a similar analysis will be performed as Primary Aim 1, except that the timeseries of the right striatum seed will be used instead of the hippocampal seed.

*Statistical Analysis for Experiments 2 and 4 (targeting the striatal network)*

i. Preliminary Aims

Preliminary Aim 1

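### The memory test's time x group x learning type interaction compares two differently measured, undefined scores, so an equal rTMS effect on both tasks can pass as network-dependent modulation

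*Combined protocol and SAP*

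**What the plan says.** Section 10.a of the combined protocol and SAP sets out the behavioural analysis twice, once for Experiments 1 and 3 and once for Experiments 2 and 4, in the same form: "Behavioral data will be submitted to a 3 x 2 x 2 ANOVA using timepoint", group and learning type as factors. The decision rule is that a significant interaction (p < 0.05) "between time, group, and learning type will confirm network-dependent modulation of each memory type". The rule states no direction and no per-task follow-up.

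The two levels of learning type are the two Weather Prediction Tasks in section 4.d.ii.

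- **WPT-F (procedural).** Cards predict an outcome with fixed probabilities. "After each prediction, the subject receives corrective feedback", and "The task has 200 trials, with breaks after every 50 trials". No later test phase is described. Section 10.a agrees when it defines the task-based connectivity model: "For the WPT-F, this will include both the choice phase and the feedback phase during learning".
- **WPT-O (declarative).** Card sets and outcomes are shown together first. "After all pairs are shown the cards are again shown and the participant is asked to remember which feedback outcome" belongs to each set. The number of retrieval items is not given.

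Section 9.b lists "Pre-to-Post rTMS differences in WPT-F scores" and the matching WPT-O line as separate secondary outcomes. It does not say whether a response is scored against the optimal answer or against the outcome that occurred, which trials count, or how the two tasks are put on one scale.

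**The concern.** A three-way interaction between two tasks means something only if a unit of change is the same in both. Here the WPT-F score probably averages over the climb from chance, whereas WPT-O is read after learning. If WPT-F is also scored against the outcome that occurred, a perfect learner still misses many trials. Either feature shrinks a true gain on WPT-F relative to the same gain on WPT-O.

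A general effect of stimulation on learning would then appear as a larger change on WPT-O. In Experiment 1 that resembles the declarative advantage expected in the Précis (Design). In Experiment 2, which targets the striatal network, the same pattern points to the non-targeted memory type, yet the undirected rule would still count it as confirmation. Whether effects are specific to one memory system is central to the study, and this is its only stated decision rule for memory.

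**Working it through.** The plan gives no power, effect size or error rate for the behavioural test, so there is no stated figure to reproduce. Section 10.b sizes each experiment on functional connectivity only.

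**Inputs from the documents.** 13 per group (10.b); three time points, two groups and two tasks (10.a); 200 WPT-F trials in blocks of 50; example card probabilities 0.2, 0.4, 0.6 and 0.8 (4.d.ii).

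**Assumed inputs.** Mean learned accuracy 0.25 above chance, between-person SD 0.08, within-person SD 0.04, exponential learning with constant τ of 50 to 100 trials, 40 to 200 WPT-O items. Active rTMS adds the same amount to learned accuracy A in both tasks at both post-baseline visits.

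**Step 1: ceiling under the example probabilities.** There are 4 + 6 + 4 = 14 one- to three-card sets. Adding log-odds across independent cards, two sets (0.2 with 0.8, and 0.4 with 0.6) come to exactly 0.5 and have no optimal answer. The best possible match to the actual outcome averages 0.698 over the 14 sets. For single cards it is (0.8 + 0.6 + 0.6 + 0.8)/4 = 0.70.

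**Step 2: how much of a gain each score shows.**

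- WPT-O score = 0.5 + A, so it shows the full gain.
- WPT-F, percent optimal over all trials = 0.5 + kA, with k = 1 − (τ/200)(1 − e^(−200/τ)). For τ = 50, k = 1 − 0.25 × 0.982 = 0.75. For τ = 100, k = 1 − 0.5 × 0.865 = 0.57.
- WPT-F, scored against the actual outcome = 0.5 + (2 × 0.70 − 1)kA = 0.5 + 0.4kA. The multiplier is 0.30 (τ = 50) or 0.23 (τ = 100).

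An equal latent gain of 0.10 therefore moves WPT-O by 0.10. It moves WPT-F by 0.075 or 0.057 with optimal scoring, and by 0.030 or 0.023 with actual-outcome scoring.

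**Step 3: the planned test.** The three-way interaction equals the group x time test on the within-person difference WPT-F minus WPT-O, F(2, 48). Share of 4,000 simulated trials with p < 0.05 at an equal gain of 0.10:

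| WPT-F scoring | τ | 40 WPT-O items | 100 items | 200 items |
|---|---|---|---|---|
| Optimal, all 200 trials | 50 | 7.7% | 8.6% | 9.7% |
| Optimal, all 200 trials | 100 | 13.4% | 18.6% | 20.9% |
| Actual outcome, all 200 trials | 50 | 30.1% | 43.9% | 50.2% |
| Actual outcome, all 200 trials | 100 | 35.8% | 52.6% | 60.8% |

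Repeat runs move these by a point or two; rounded across runs the ranges are about 8 to 20% and about 28 to 63%. With no rTMS effect on either task the rate is about 5% (4 to 6%) under every scoring.

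**Step 4: a common scale.** Restricting WPT-F to optimal scoring in the last 50 trials gives k = 1 − (τ/50)(e^(−150/τ) − e^(−200/τ)), which is 0.97 for τ = 50 and 0.82 for τ = 100. The task difference from an equal gain of 0.10 falls to 0.10 × (1 − 0.97) = 0.003 or 0.10 × (1 − 0.82) = 0.018. For gains of 0.10 to 0.15 the interaction is then significant in about 5 to 7% of trials. Dividing each task by its own baseline SD as well raises this to about 6 to 14%, because baseline SDs differ when item counts differ.

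**The case against.** The strongest reply is that the documents define no score, so any distortion comes from the reader's choice of scoring, and a sentence fixing the score would suffice. Part of this stands. The size is conditional: it is small with late-trial optimal scoring and large with actual-outcome scoring. But the rule itself is written down, is undirected, and joins a task with no described test phase to a task tested only at retrieval. That is more than missing detail.

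The plan also expects better declarative memory and possibly poorer procedural learning in Experiment 1. Unequal scaling of one common effect cannot produce changes in opposite directions, and section 9.b lists the two tasks separately, so direction would be visible. That is true, but the confirmation rule does not use the direction, and the procedural decrease is described only as possible.

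Several stronger readings are tempting and not supported:

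- **Inflated type I error.** With no effect on either task the test keeps its 5% level. The problem needs a real effect on both.
- **A fixed distortion of two- to threefold.** That follows from scoring WPT-F against actual outcomes and WPT-O against optimal answers, a pairing the documents never state.
- **Different floors.** Both tasks have a binary rain or fine response, so chance is 50% in each. Nor are the 50/50 card sets shown to be peculiar to WPT-F.
- **A known 70% ceiling.** The card probabilities are given only as an example.

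**Conclusion.** The concern holds in a conditional form. As written, the interaction rule can label an equal effect of rTMS on both tasks as network-dependent modulation. With 13 per group and an equal latent gain of 0.10, the chance is about 8 to 20% with all-trial optimal scoring and about 28 to 63% with actual-outcome scoring, compared with about 5% when neither task is affected. These figures rest on the learning constants, SDs and WPT-O item counts assumed above. They also rest on the inference, from the absence of any other phase, that WPT-F scores come from the learning trials.

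A reader might infer that the trial's main conclusion is at risk. It is not: memory change is a secondary outcome, and the functional connectivity primary does not use these scores. The change should be made before the behavioural data are analysed, with moderate confidence in the sizes and more in the mechanism.

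**What to change.** In section 10.a, for all four experiments:

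1. Score both tasks as percent optimal responses on card sets that have an optimal answer, leaving out any 50/50 sets. Use the last 50-trial block for WPT-F and the retrieval trials for WPT-O. Do not divide each task by its own baseline SD.
2. Report the active-minus-vertex change for each task with its confidence interval beside the interaction.
3. State the predicted direction for each experiment. Claim network-dependent modulation only when the interaction is significant and the per-task changes show that direction for the targeted network. Direction alone is not enough, because in Experiment 1 an equal gain already leans the expected way; the common scale is needed too.
4. State the number of WPT-O retrieval items, and add the score definitions to section 9.b.

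The cost is SAP wording and a short scoring program; no new data are needed. The downside is a noisier WPT-F score. If the 14 sets are shown equally often, 200 × 12/14 ≈ 171 usable trials become 50 × 12/14 ≈ 43, which roughly doubles the trial-level noise (√(171/43) ≈ 2.0). Report the all-trial WPT-F score as supportive.

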### iii. MRI

We estimate a maximum of 2 hours for each scan in all experiments. Because scanner malfunctions and subsequent loss of data are common we will not report these as unexpected problems at the time of occurrence, but only at the time of continuing review. Subjects whose data are lost due to scanner malfunctions will be rescheduled, if possible.

#### *1. MRI Anatomical scanning*

All subjects will have anatomical (MPRAGE) scans at baseline, 24-hours, and 2-weeks after rTMS. Participants who have not had one in the past year will receive a standard clinical MRI scan of the head, which will be submitted to the Diagnostic Radiology Department CC for interpretation. Depending on the requirement for a clinical scan, this phase will take 10-30 min.

#### *2. Resting-State FC*

During scanning, participants will be instructed to lie motionless with open eyes fixated on a cross that is presented on a screen visible through a mirror attached to the MR head coil (approximately 10 min).

#### *3. Task-Based FC*

During scanning, participants will perform both versions of the WPT and tbFC will be measured. During the feedback version of the task, when a response is required, participants will respond using one of two buttons on a button box inside the scanner. Participants will respond verbally during the retrieval phase of the WPT-O.

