## **9. Outcome Measures**

### **a. Primary outcome measures**

- Pre-to-Post rTMS differences in rsFC and tbFC within the targeted memory network.

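### WPT-F is answered by button and WPT-O retrieval by speech in the scanner, which can add motion noise to one primary tbFC measure and ties response mode to learning type in the behavioural ANOVA

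*Combined protocol and SAP*

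**What the plan says.** Section 4.d.iii.3 (Task-Based FC) has both task versions performed during scanning. For WPT-F, "participants will respond using one of two buttons on a button box inside the scanner". For the observational version, "Participants will respond verbally during the retrieval phase of the WPT-O".

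Section 10.a builds tbFC from a general linear model containing the seed time series "along with a regressor indicating when the task is occurring". On the phases that enter it: "For the WPT-F, this will include both the choice phase and the feedback phase during learning". And: "For the WPT-O, this will include the observational trials and the retrieval trials". The phase in which participants speak is therefore in the WPT-O estimate.

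Section 9.a lists the primary outcome as "Pre-to-Post rTMS differences in rsFC and tbFC within the targeted memory network". Section 9.b makes the WPT-O and WPT-F scores secondary. The behavioural ANOVA in section 10.a crosses three timepoints and two groups with "learning type (procedural and declarative) as factors". A time by group by learning-type interaction at p < 0.05 is taken as confirmation that stimulation acts on memory in a network-dependent way.

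Section 4.d.ii describes WPT-O retrieval as a two-way choice: "the participant is asked to remember which feedback outcome (rain or fine) goes with that set of cards". No reason is given for using speech.

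**The concern.** Two separate things are at stake.

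The first is noise in a primary measure. Speaking moves the jaw and can move the head while images are being acquired. If that raises the variance of WPT-O tbFC change, precision is lost in one component of the primary outcome, with only 13 participants per group.

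The second is interpretation of a secondary result. Each level of learning type is represented by one task, and each task has its own response mode. If stimulation changes motor output, and manual and spoken responding are not changed alike, the difference appears as a learning-type effect. No analysis of the collected data could separate the two. This matters most in Experiments 2 and 4, where the active site is M1 and the control is vertex.

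**Working it through.** The plan gives no figure on this point, so the main check is to set its provisions side by side.

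| Item | WPT-F | WPT-O | Source |
|---|---|---|---|
| Learning type represented | procedural | declarative | 10.a |
| Answer format | rain or fine | rain or fine | 4.d.ii |
| Response in scanner | button | speech, retrieval only | 4.d.iii.3 |
| Phases in tbFC model | choice and feedback | observation and retrieval | 10.a |
| Same in both arms and at all visits | yes | yes | 4.a, 4.d |

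**Primary outcome.** The quantity of interest is change from before to after stimulation within a task, active against vertex. Response mode is constant across arms and visits, so its average effect cancels from that comparison. What can remain is added variance in WPT-O tbFC. rsFC is recorded without a task and WPT-F tbFC without speech.

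**Size of the noise (assumed).** The documents give no variance for WPT-O tbFC and no estimate of speech motion. If speech multiplies the variance of the change by k, a standardised effect d becomes d/√k. Taking d = 0.75 from section 10.b:

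- k = 1.10: 0.75/√1.10 = 0.72
- k = 1.25: 0.75/√1.25 = 0.67
- k = 1.50: 0.75/√1.50 = 0.61

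Both inputs are assumptions for this measure. The 0.75 comes from pilot hippocampal FC with the precuneus and medial occipital cortex. Section 1.c describes the laboratory's evidence as rsFC and says that the effect on tbFC is unknown.

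**Behavioural interaction (assumed).** Take each participant's pre-to-post change in WPT-F minus that in WPT-O. Let each change have SD 1 and let the between-task correlation be r. The contrast then has SD √(2(1 − r)). Suppose there is no memory effect and active stimulation shifts only the button-press task, by δ. The standardised difference between arms is δ/√(2(1 − r)). With 13 per group, a two-sided t test at 0.05 has 24 df and noncentrality equal to that difference times √(13/2). For δ = 0.5 and r = 0.5 the SD is 1, the noncentrality is 0.5 × 2.55 = 1.27, and the probability of a significant result is 0.23.

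| δ (SD of change) | r = 0 | r = 0.3 | r = 0.5 |
|---|---|---|---|
| 0 | 0.05 | 0.05 | 0.05 |
| 0.25 | 0.07 | 0.08 | 0.09 |
| 0.5 | 0.14 | 0.18 | 0.23 |
| 0.75 | 0.26 | 0.34 | 0.45 |
| 1.0 | 0.41 | 0.54 | 0.69 |

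This uses two of the three timepoints for simplicity. The first row is the important one: if response mode acts equally in both arms, the error rate stays at 0.05. The other rows show what a motor-only shift would do if there were one. The documents give no value for δ or r.

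**The case against.** A reader might infer that the primary comparison is biased, or that differences in tbFC between WPT-F and WPT-O are confounded with hand versus speech. The documents support neither. Response mode is balanced across arms and visits, and no WPT-F versus WPT-O contrast of tbFC is specified. Speech is also absent from the observation phase.

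A reader might also infer that M1 stimulation will produce a false interaction. That is only a possibility. The effect would have to last to testing 12 to 48 hours after the final session, or to the two-week follow-up. It would also have to change the task score. The score is not defined as a reaction time and no response deadline is given; if it is choice accuracy, slightly altered finger movement has no obvious route to it. The target is the part of M1 most connected to the right striatum, and neither a hand area nor the responding hand is specified. Speech is motor output too. In Experiments 1 and 3, where the site is PPC, the M1 argument does not apply.

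The statistical section describes no motion handling for any scan, so its silence on speech does not show that motion will go uncorrected. The tasks also differ in feedback and in having separate study and test phases, so matching the response would not by itself isolate memory type.

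All of this stands, and it limits the point. It does not explain why a two-way answer has to be spoken when the button box is already in the scanner. Nor is a lasting effect excluded: the plan itself looks for effects at two weeks and waits at least 30 days for washout before rescheduling (section 4.b.i).

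**Conclusion.** The point holds in a limited form. Spoken retrieval trials enter one component of the primary outcome and can add motion noise to it, without by themselves biasing active against vertex. In the secondary ANOVA, response mode is completely aliased with learning type, so a significant three-way interaction cannot exclude a motor contribution, chiefly in Experiments 2 and 4.

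The size of both effects is unknown. The fall from 0.75 to between 0.72 and 0.61, and the probabilities of 0.07 to 0.69, are consequences of assumed inputs and not estimates for this trial. The interaction argument also assumes that the analysed WPT scores come from the in-scanner runs, which sections 4.d.ii and 4.d.iii.3 imply but do not state. This is an avoidable weakness that is cheap to remove before data are collected; it does not invalidate the primary comparison.

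**What to change.** In section 4.d.iii.3, replace spoken WPT-O retrieval with a rain or fine response on the same two-button box, using the same hand as WPT-F, at all three sessions. Answers can then be logged automatically.

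The cost is one sentence and a small change to the task script, with no added equipment, visits or participants. The downside is that WPT-O retrieval then includes a manual response and hand-motor activity, including in the M1 experiments, and is less comparable with any earlier spoken version. The remaining task differences mean that the three-way interaction should still be read with caution, and section 10.a should say so.

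If speech has to be kept, the plan should give the reason and state in advance how motion during spoken trials is handled, for example by also estimating WPT-O tbFC from the observation trials alone.
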